#### **4.4.2 Male Contraception**

Male participants must agree to take all necessary measures to avoid causing pregnancy in their sexual partners during the study and for 3 months after the last dose of study drug. Medically acceptable contraceptives include surgical sterilization (such as a vasectomy) and a condom used with a spermicidal gel or foam. Contraceptive measures such as Plan BTM, sold for emergency use after unprotected sex, are not acceptable methods for routine use.

Male subjects should not donate sperm during the study and for 30 days after the last dose of study drug.

#### **4.5 Discontinuation of Subjects**

A subject may withdraw, or their parent, guardian, or LAR may withdraw the subject, from the study drug administration and/or the study at any time for any reason without prejudice to their future medical care by the physician or at the hospital. The investigator or sponsor may withdraw the subject at any time (e.g., in the interest of subject safety). The investigator is encouraged to discuss withdrawal of a subject from study drug with the Medical Monitor when possible unless due to progression to an IV anesthetic drug (a 3rd line treatment) for seizure suppression.

### Study drug discontinuation

Subjects who discontinue study drug without a taper, e.g., takes study drug for less than 2 hours or progresses to an IV anesthetic (a 3rd line treatment) for seizure suppression or discontinues the study medication due to safety reasons will continue in the study and still have the in-patient follow-up day and the week 2, 3 and 4 follow-up visits/contacts.

### Study withdrawal

Subjects who early terminate from the study, e.g. due to consent withdrawn, any outstanding screening procedures and the evaluations listed for the Early Termination Visit in Table 1 should be completed when early termination is being considered and as close as possible to the end of the study drug administration.

#### **4.5.1 Subject Withdrawal Criteria**

All subjects reserve the right to withdraw from the clinical study at any time, as stated in the informed consent form. The investigator may also discontinue subjects from the clinical study for any of the following reasons:

1. The subject has persistent ventilatory depression that results in a SpO2 < 90% or ETCO2 > 50 mmHg (measured using nasal cannula monitor) despite the use of airway maneuvers including assisted ventilation. Standard airway maneuvers to treat sedation-induced upper airway obstruction (jaw thrust, chin lift, or supraglottic device such as a laryngeal mask airway) or hypoventilation (ventilation assisted with a mask or supraglottic device) would be instituted at the discretion of the physician monitoring the patient in order to maintain SpO2 > 90% and ETCO2 < 51 mmHg. If the subject does not respond to these methods, the subject would be discontinued
2. ECG evidence of QT prolongation (QTcF > 500 msec, or an increase of QTcF > 60 msec above baseline to a value > 480 msec on the 12-lead ECG, confirmed on a repeat 12-lead ECG taken after resting at least 5 minutes in a supine or semi recumbent position after the original finding of prolonged QTcF)
3. Kidney function impairment such that eGFR ≤ 45 mL/min and subject is not starting dialysis
4. Any other adverse event or safety issue (e.g., severe persistent hypotension/hypertension or tachycardia/bradycardia) that suggests it is not in the subject's best interest to continue to receive study drug
5. Rash that is clinically significant and considered to be related to the study drug (e.g., morbilliform, urticarial, papular)
6. Subject experiences an SAE considered to be related to the study drug

Decisions to discontinue the study will be made at each participating site by the principal investigator. If feasible, the reason for discontinuation should be discussed with the Medical Monitor prior to subject discontinuation unless due to the progression to an IV anesthetic drug (a 3rd line treatment) for seizure suppression.

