Updated the Study Flow Diagram to reflect the revised dosing regimen.	Figure 1
Added clarity for subjects who discontinue by separating subjects who discontinue from study drug and subjects who withdrawal from the study	Section 4.5
Removed duplicate text describing prior concomitant treatment; revised collection requirements for concomitant treatment	Section 5.1
Expanded the guidance on administration of background oral AEDs if their administration is interrupted during the study	Section 5.2.2
Added statement that the Investigator's Brochure has not been updated with the 1 mg/mL, ganaxolone IV solution formulation at this time but will be amended with the annual update	Section 8.2.1
Updated timeline for entering data into EDC	Section 9.1
Added exploratory endpoints to assess pressor administration and treatment of severe cardiovascular and respiratory events	Section 9.7.3
Added that APACHE or APACHE 2 score may be used as a prognostic tool in calculating mortality	Section 9.8

Updated the Study Decision Tree	Appendix 1
Added Summary of Changes Table from Protocol Amendment 3	Appendix 2
Revisions made in the document to standardize text throughout the protocol such as: study drug initiation for dose initiation and dose start; study drug discontinuation for study drug stop; 24-hour post taper to in-patient follow-up day; subject for participant	
Additional grammatical, typographical errors and formatting revisions have been made in the document but are not identified here	

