#### Study Follow-up and Discontinuation:

Subjects who discontinue study drug without a taper, e.g., takes study drug for less than 2 hours or progresses to an IV anesthetic drug (a 3rd line treatment) for seizure suppression or discontinues the study medication due to safety reasons will continue in the study and still have the in-patient follow-up and the week 2, 3, and 4 follow-up visits/contacts.

Subjects who early terminate from the study, e.g., due to consent withdrawn, should have the early termination procedures completed when early termination is being considered and as close as possible to the end of the study drug administration.

All subjects, except those who are early terminated from the study, will have the in-patient follow-up day and the follow-up visits/contacts at Weeks 2, 3, and 4. If the subject remains hospitalized these visits will be done in person but if the subject has been discharged these contacts will be conducted via telephone call. Even if a subject has been discharged, efforts will be made to have the subject return so at least one of the visits will be conducted in-person. These visits will be conducted weekly, starting approximately  $7 \pm 3$  days after the in-patient follow-up day.

During these visits/calls, the site will follow-up on all serious adverse events (SAEs) and non-serious adverse events (AEs), AE resolution that occurs, and concomitant medications. In total, each subject will be followed for approximately 4 weeks.

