#### **5.2 Concomitant Treatment**

Concomitant treatment refers to all treatment taken between the date of the first dose of study drug and the end of the follow-up period, inclusive. However, the collection requirements will differ depending on the subject's treatment progression as defined below.

- All concomitant medications will be collected through the in-patient follow-up day
- During the weekly follow-up visits, only concomitant medications associated with ongoing AEs and new AEs assessed by the investigator to be related to study drug will be recorded
- All concomitant medications associated with SAEs regardless of relationship to study drug will be recorded from the time of study drug initiation through the last follow-up visit/contact
- In addition, for subjects who stop study drug administration without a taper but continue with the follow-up visits, any IV anesthetic agents (midazolam, propofol, thiopental, pentobarbital, or ketamine) that were started on the in-patient follow-up day should be followed through the last follow-up visit/contact
- At the time that early termination from the study is being considered, prior to discontinuation as much information as is available should be recorded on the concomitant medications associated with ongoing AEs/SAEs and new AEs/SAEs, especially those that may have led to the early termination

Concomitant treatment information must be recorded on the appropriate eCRF page. For some of the concomitant medications only the highest dose administered will be required in the eCRF. Reference the eCRF Completion Guidelines for guidance

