### **5.2.2 Prohibited Treatment**

As per the exclusion criterion in Section 4.2, the only allowable concurrent 2nd line IV AED therapies to treat the current episode of SE are fosphenytoin/phenytoin, valproic acid, levetiracetam, lacosamide, or brivaracetam. Administering fosphenytoin and/or phenytoin will be counted as one (1) AED. These drugs can be used alone or in combination with each other. If the subject is receiving oral AED therapy to manage a subject's chronic medical condition, for example, epilepsy, migraine, or neuropathic pain, that therapy is acceptable and should continue unchanged, if feasible and medically justified. This prophylactic treatment does not count towards the SE treatment failures required to qualify for this study. If any of these oral AED medications had to be interrupted around the time of the current SE episode, it is recommended that they would be re-started 10 hours after study drug initiation, if medically acceptable. Also, subjects who have been enrolled in another clinical study for SE are required to have a reasonable expectation that the other investigational drug has been cleared from their system, that is, that five half-lives have elapsed. Subjects on IV AEDs that are standard of care can be enrolled in the study. Subjects who have taken exogenous allopregnanolone or ganaxolone previously are not eligible for the study.

If a subject progresses at any time during the study to an IV anesthetic drug (a 3rd line treatment; e.g. midazolam, propofol, thiopental, pentobarbital, or ketamine and/or 4th line treatment; e.g., immunosuppressants, magnesium) for seizure suppression, study drug administration will be discontinued, however the subject will continue with the in-patient follow-up day and the week 2, 3, and 4 follow-up visits.

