A subject who discontinues or early terminates from the study (e.g., due to consent withdrawn) should have the early termination procedures completed when early termination is being considered and as close as possible to the end of the study drug administration. A list of early termination assessments can be found in Table 1.

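### Protocol Section 4.5.1 permits removal from the study for six safety reasons, in conflict with Section 4.5 and the Synopsis, which keep safety stops of study drug in follow-up to Week 4

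*Protocol*

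**What the plan says.** Protocol Section 4.5.1 (Subject Withdrawal Criteria) opens its list with "The investigator may also discontinue subjects from the clinical study for any of the following reasons". The six reasons are persistent ventilatory depression, confirmed QTcF prolongation, eGFR at or below 45 mL/min without a start of dialysis, any other adverse event or safety issue, clinically significant drug-related rash, and a drug-related SAE. The section closes with "Decisions to discontinue the study will be made at each participating site by the principal investigator".

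Section 4.5, under Study drug discontinuation, gives a different rule. A subject who stops without a taper, including one who "discontinues the study medication due to safety reasons will continue in the study and still have the in-patient follow-up day", also keeps the Week 2, 3 and 4 contacts. The Synopsis (Study Follow-up and Discontinuation) repeats this and adds: "All subjects, except those who are early terminated from the study, will have the in-patient follow-up day", together with the weekly contacts.

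Section 4.5 treats study withdrawal as a separate category, with withdrawn consent as its example. Section 7.1.3 describes what follows: "A subject who discontinues or early terminates from the study (e.g., due to consent withdrawn) should have the early termination procedures completed".

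The opening paragraph of Section 4.5 is itself loose. It lets the subject or representative leave study drug, the study, or both. It then lets the investigator or sponsor withdraw a subject for safety without saying from which.

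**The concern.** One event, such as a QTcF above 500 msec or a drug-related SAE, leads to full follow-up under Section 4.5 and may lead to study exit under Section 4.5.1. Two sites could handle identical subjects differently and both be within the protocol.

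The subjects who could leave are those with safety events, so any loss would be informative. What is at stake is scheduled safety and outcome follow-up after drug stop in the subjects for whom it matters most. The record of who left the drug and who left the study is also affected.

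**Working it through.** The plan gives no figure to reproduce. The check is a comparison of texts, a count of scheduled collections, and a test of whether the wording reaches the SAP.

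**1. The rules side by side**

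| Place in protocol | What stops | Follow-up afterwards | Force |
|---|---|---|---|
| 4.5, Study drug discontinuation; Synopsis | Study drug, for safety | In-patient day and Weeks 2, 3, 4 | Will |
| 4.5.1 lead-in and close | The clinical study, for six safety reasons | None stated | May |
| 4.5, opening paragraph | Not specified, for safety | None stated | May |
| 7.1.3, last paragraph | The study (discontinues or early terminates) | Early-termination procedures | Should |
| Synopsis exception | The study (early terminated) | Exempt from in-patient day and weekly contacts | Stated rule |

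The 4.5 rule is written for stops without a taper. Tapered subjects get the same follow-up under the Synopsis and Section 7.1.3, so that limit does not remove the conflict.

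**2. What was meant**

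Four things point to study drug.
- Reason 4 in 4.5.1 turns on whether the subject should go on receiving study drug.
- The opening of 4.5 asks investigators to discuss withdrawal from study drug with the Medical Monitor, except on progression to an IV anesthetic. The close of 4.5.1 has nearly the same rule and the same exception, but applies it to discontinuing the study. Yet Section 5.2.2 says of subjects who progress to an anesthetic that "study drug administration will be discontinued, however the subject will continue with the in-patient follow-up day".
- The Amendment 4 summary of changes gives the aim for Section 4.5 as "separating subjects who discontinue from study drug and subjects who withdrawal from the study". This is evidence of intent only.
- Section 6.2.4 withdraws a subject from the study after a code break but states that safety follow-up continues. Section 4.5.1 has no such clause.

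**3. Collections no longer scheduled, per subject terminated under 4.5.1**

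The source is Protocol Table 1 with footnotes g, h, p, q, r and t. Early termination leaves one collection, so the share no longer scheduled is (planned − 1) / planned.

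| Assessment | At stop | 24 h after | Weekly | Planned | Not scheduled |
|---|---|---|---|---|---|
| CGI-S, CGI-I, seizure questions, MRS (each) | 1 | 1 | 3 | 5 | 4/5 = 80% |
| Chemistry with eGFR | 1 | 1 | 1 (if possible once discharged) | 3 | 2/3 = 67% |
| ECG | 1 | 1 | 0 | 2 | 1/2 = 50% |

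The PK sample 24 hours after drug stop also falls away. These are counts for one hypothetical subject. The documents give no rate for the six events, so no expected number of subjects can be computed.

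**4. Does the wording reach the SAP tables?**

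- SAP Sections 1 and 3 name Amendment 3 (Version 4.0) as the protocol followed. SAP Appendix 1 has an 18-hour taper; the current protocol has 12 hours.
- SAP Section 1 sets cohorts at target doses of 713, 650 and 500 mg/day.
- The current Day 1 dose for subjects of at least 40 kg (Protocol Table 2) is 30 + 80×2 + 40×10 + 20×12 = 30 + 160 + 400 + 240 = 830 mg, which matches no cohort.

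The subjects in the SAP tables therefore appear to have been dosed under previous amendments, whose Section 4.5.1 lead-in is not in the documents.

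**The case against.** The strongest reply is that this is a drafting slip. The mandatory rule addresses this very case and is stated in both 4.5 and the Synopsis, while 4.5.1 only says may. The opening of 4.5 already allows withdrawal for safety, so the ambiguity does not arise in 4.5.1 alone. The Early Termination column still collects ECG and chemistry, QTcF prolongation must be confirmed on a repeat tracing, and both tests can be done at any time if medically indicated. Section 8.2.4 and the Synopsis collect SAEs through follow-up regardless of relationship, and related SAEs found later must still be reported.

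Most of this stands, and it sets the severity. It does not remove the conflict: a permission to end participation is still incompatible with a rule that participation continues. The loose opening of 4.5 is a reason to widen the fix. SAE collection remains in doubt because Section 8.1 asks, for early terminators, for what is available before discontinuation.

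A reader might draw stronger conclusions that the documents do not support.
- *That these subjects must leave the study.* Reason 1 ends by saying that a non-responding subject would be discontinued, but the lead-in governing the list is permissive.
- *That the 24-hour primary window is cut short*, for example by 24 − 2 = 22 hours after a stop at hour 2. This needs study exit at the moment of drug stop and no later recording. Section 5.2 says "At the time that early termination from the study is being considered, prior to discontinuation as much information as is available should be recorded", but that bullet concerns medications associated with adverse events. It sets no general cut-off on recording anesthetics.
- *That 4.5.1 disables the rule for following abnormal values to resolution.* Section 8.1.5 words that rule for subjects who complete the study without an IV anesthetic. It thus also omits anesthetic progressors who remain in the study, and its scope was not set by 4.5.1.

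**Conclusion.** Wrong as written: an internal contradiction, of low severity. Section 4.5.1 permits, without requiring, study exit for six safety reasons where Section 4.5 and the Synopsis keep the subject in follow-up to Week 4.

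The size is known only per subject, as counted above, and assumes a site that applies 4.5.1 literally and then the early-termination schedule. The number of such subjects is unknown and may be zero.

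A reader might also infer that percentages in the SAP's summaries would shift. The documents do not show this. The SAP follows Amendment 3, its cohort doses do not match the current regimen, and nothing shows that the current 4.5.1 wording governed any subject it summarises. SAP Section 4.8 is in any case descriptive, with no inferential efficacy test.

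**What to change.** Five wording changes in the protocol:
1. Section 4.5.1, lead-in: *The investigator may discontinue study drug for any of the following reasons*.
2. Section 4.5.1, closing paragraph: begin *Decisions to discontinue study drug*.
3. Section 4.5.1, new sentence: *These subjects remain in the study for the in-patient follow-up day and the Week 2, 3 and 4 contacts unless consent is withdrawn.*
4. Section 4.5, opening paragraph: in the sentence on withdrawal by the investigator or sponsor, insert *from study drug* after *subject*.
5. Section 7.1.3, last paragraph: delete *discontinues or*, so that the early-termination procedures apply only to subjects who early terminate from the study.

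Changes 4 and 5 are needed because correcting 4.5.1 alone would leave the same ambiguity in those two places. The cost is text only. No stopping criterion changes, the right to withdraw consent is untouched, and the follow-up contacts are already planned.

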#### **4.5.2 Reasons for Discontinuation**

The reason for discontinuation must be determined by the investigator and recorded in the subject's medical record and in the eCRF. If a subject is withdrawn for more than one reason, each reason should be documented in the source document and the most clinically relevant reason should be entered in the eCRF.

Reasons for discontinuation include but are not limited to:

- Adverse event
- Protocol deviation
- Consent withdrawal
- Lost to follow-up
- Lack of efficacy
- Death
- Physician decision
- Other (must be specified in the subject source document and eCRF)

#### **4.5.3 Subjects Lost to Follow-up Prior to Last Scheduled Visit**

A minimum of three documented attempts must be made to contact any subject lost to follow-up at any timepoint prior to the last scheduled contact (office visit or telephone contact). At least one of these documented attempts must include a written communication sent to the subject's last known address via courier or mail (with an acknowledgment of receipt request) asking that they return to the site for final safety evaluations. If a contact is not made the subject should be classified as Lost to Follow-up in the eCRF. However, if contact is made but the subject refuses or is unable to come to the final safety evaluation, they should be classified as Other and the reason documented in the eCRF.

### **5. PRIOR AND CONCOMITANT TREATMENT**

#### **5.1 Prior Treatment**

Prior treatment includes all non-study treatment received within 30 days prior to the first dose of study drug (or pharmacokinetic equivalent of five half-lives, whichever is longer). Treatments including but not limited to herbal treatments, vitamins, surgical implants (such as Vagus nerve stimulator), and prescribed medications, if available, must be recorded on the appropriate eCRF page.

#### **5.2 Concomitant Treatment**

Concomitant treatment refers to all treatment taken between the date of the first dose of study drug and the end of the follow-up period, inclusive. However, the collection requirements will differ depending on the subject's treatment progression as defined below.

- All concomitant medications will be collected through the in-patient follow-up day
- During the weekly follow-up visits, only concomitant medications associated with ongoing AEs and new AEs assessed by the investigator to be related to study drug will be recorded
- All concomitant medications associated with SAEs regardless of relationship to study drug will be recorded from the time of study drug initiation through the last follow-up visit/contact
- In addition, for subjects who stop study drug administration without a taper but continue with the follow-up visits, any IV anesthetic agents (midazolam, propofol, thiopental, pentobarbital, or ketamine) that were started on the in-patient follow-up day should be followed through the last follow-up visit/contact
- At the time that early termination from the study is being considered, prior to discontinuation as much information as is available should be recorded on the concomitant medications associated with ongoing AEs/SAEs and new AEs/SAEs, especially those that may have led to the early termination

Concomitant treatment information must be recorded on the appropriate eCRF page. For some of the concomitant medications only the highest dose administered will be required in the eCRF. Reference the eCRF Completion Guidelines for guidance

### **5.2.1 Permitted Treatment**

Ganaxolone IV solution will be administered as adjunctive therapy to the hospital's standard of care. Any medication classified by the hospital as per the standard of care will be acceptable. Anything outside of the standard of care should be discussed with the Medical Monitor.

